### **8.2.7 Clinical Safety Laboratory Assessments**

- See [Appendix 3](#) Table 13 for the list of clinical laboratory tests to be performed and to the Table 1 SoA for the timing and frequency. See [Appendix 3](#) Table 13 and Table 14, respectively for local and central laboratory assessments.
- The Investigator must review the laboratory report, document this review, and record any clinically relevant changes occurring during the study in the AE section of the eCRF. The laboratory reports must be filed with the source documents. Clinically significant abnormal laboratory findings are those that are not related to HFrEF or any other pre-existing condition at the time of enrollment, unless judged by the Investigator to be more severe than expected for the subject's condition.
- All laboratory tests with values considered clinically significantly abnormal, relative to baseline values, within 30 days after the dose of study treatment should be repeated until the values return to normal or baseline or are no longer considered clinically significant by the Investigator or Medical Monitor.
  - If such values do not return to normal/baseline within a period judged reasonable by the Investigator, the etiology should be identified, and the Sponsor notified.
  - All protocol-required laboratory assessments, as defined in [Appendix 3](#), must be conducted in accordance with the laboratory manual and the Table 1 SoA.
  - If laboratory values from non-protocol-specified laboratory assessments performed at the institution's local laboratory require a change in subject management or are considered clinically significant by the Investigator (e.g., SAE or AE or dose modification), then the results must be recorded in the eCRF.

### **8.2.8 Immunogenicity Assessments**

Antibodies to JK07 will be evaluated in serum samples collected from all subjects according to the Table 1 SoA. Additionally, serum samples should also be collected at the final visit from subjects who discontinued study treatment or were withdrawn from the study. These samples will be tested by the Sponsor or Sponsor's designee.

Serum samples will be screened for antibodies binding to JK07. Samples which show a positive response in the screening assay will be evaluated using a confirmatory ADA assay, and the confirmed positive samples will be reported and their potential for neutralizing activity will be explored. Other analyses will be performed to verify the stability of JK07 and to further characterize the immunogenicity of JK07.

The detection and characterization of antibodies to JK07 will be performed using a validated assay method by or under the supervision of the Sponsor. Antibodies may be further characterized and/or evaluated for their ability to neutralize the activity of the study treatment(s). Samples may be stored for a maximum of 10 years (or according to local regulations) following the last subject's last visit for the study at a facility selected by the Sponsor to enable further analysis of immune responses to JK07.

### **8.2.9 Two-dimensional Transthoracic Echocardiography**

Left ventricular and hemodynamic performance indices measured by 2D-TTE will be explored. Potential effects of JK07 will be evaluated as change from baseline and will be compared with changes from baseline in subjects receiving placebo.

On Day 1, 2D-TTE will be performed locally following American Society of Echocardiography guidelines and recommendations, pre-dose and at 6 hours  $\pm$  30 minutes, and on Day 2 at 30 hours  $\pm$  30 minutes following completion of the dosing infusion, and at subsequent times described in the [Table 1](#) SoA.

The full examination will be evaluated locally for safety and will be digitally transferred to the Central Laboratory for centralized evaluation and centralized calculation of the measurements. Measurements taken by the Central Laboratory will include but are not limited to: ejection fraction, multiple LV chamber dimensions, including LVESV, LVEDV, as well as multiple calculated monitoring parameters using velocity and flow measurements including SV, CO, and E/e' calculations (Please see [Appendix 5](#) for detailed listing).

## **8.3 Safety Monitoring and Reporting**

### **8.3.1 Adverse Events**

In accordance with the ICH E2A guideline, and 21 Code of Federal Regulations (CFR) §312.32, an AE is defined as any untoward medical occurrence in a clinical study subject administered a pharmaceutical product, which does not necessarily have a causal relationship with this treatment. An AE can therefore be any unfavorable and unintended sign (including an abnormal laboratory finding), symptom, or disease (new or exacerbated) temporally associated with the use of study treatment.

This includes the following:

- Any abnormal laboratory test results relative to baseline values (hematology, clinical chemistry, or urinalysis) or other safety assessments (e.g., ECG, radiological scans, vital signs measurements), including those that worsen from baseline, considered clinically significant in the medical and scientific judgment of the Investigator (i.e., not related to progression of underlying disease).
- Exacerbation of a chronic or intermittent pre-existing condition including either an increase in frequency and/or intensity of the condition.
- New conditions detected or diagnosed after study treatment administration even though it may have been present before the start of the study.
- Signs, symptoms, or the clinical sequelae of a suspected drug-drug interaction.
- Signs, symptoms, or the clinical sequelae of a suspected overdose of either study treatment or a concomitant medication. Overdose per se will not be reported as an AE/SAE unless it is an intentional overdose taken with possible suicidal/self-harming intent. Such overdoses should be reported regardless of sequelae.

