In the same study dose-independent minimal to moderate myocardial degeneration was observed during autopsy. The current phase 1 study requires 2D-TTE monitoring at screening, during the hospital stay and at multiple follow-up visits to check for improvement or worsening of indexes of myocardium contractility.

In the same study, there were also a dose-independent minimal JK07-related increases in cardiac troponin I (cTnI) at 10 and 30 mg/kg on Day 8 and at 30 mg/kg on Day 28, with recovery by Day 56. Although the highest cTnI values occurred in a control animal at multiple time points (Animal No. 1504, Days -7 through 28), the increased frequency of values at 10 and 30 mg/kg suggested a possible JK07-related effect. Since the increases in cTnI could potentially be correlated with microscopic findings of myocardial degeneration, this phase 1 study will monitor a wide panel of safety and efficacy biomarkers which are useful to carefully detect any effect of JK07 on myocardium (NT-proBNP, total BNP, high-sensitivity C-reactive protein [hsCRP], troponin-I, high-sensitivity [hs]-troponin T, creatine phosphokinase [CPK], creatine kinase-muscle/brain [CPK-MB]). It should be noted that NRG-1 directly activates NT-proBNP expression which complicates the normal relationship between the levels of that biomarker and cardiomyocyte damage. Changes in this biomarker, therefore, need to be interpreted with caution and in the context of the totality of the data.

Systemic exposure of JK07 will be measured by utilizing an immunoassay targeting two different domains of JK07. The capture antibody will be specific for the NRG-1 sequence of JK07, and the detection antibody will be specific for the antibody domain, using a biotinylated anti-idiotype antibody binding to the variable sequence of JK07 antibody domain. Use of the two antibodies together will provide exposure data specifically for the intact JK07 molecule over time across JK07 dose levels. NRG-1 peptide cleaved from JK07, with or without the linker, is expected to have a very short half-life in circulation and to be below detectable levels in circulation.

As JK07 is a monoclonal antibody, anti-drug antibody (ADA) response for JK07 will be evaluated periodically throughout the study with blood samples collected as early as 3 days after dose administration.

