### **8.3.7      Recording AEs and SAEs**

When an AE/SAE occurs, it is the responsibility of the Investigator to review all documentation (e.g., hospital progress notes, laboratory reports, and diagnostics reports) related to the event.

The Investigator will then record all relevant AE/SAE information in the eCRF. Each event must be recorded separately.

It is not acceptable for the Investigator to send photocopies of the subject's medical records in lieu of completion of the AE/SAE eCRF page. There may be instances when copies of medical records for certain cases are requested. In this case, all subject identifiers, except for the subject number, will be redacted on the copies of the medical records before provided.

Each AE is to be evaluated for:

- AE diagnosis or syndrome (if not known, signs or symptoms)
- Dates of onset and resolution
- Severity (including grade changes as per the CRF completion guidelines)
- Causal relationship with study drug or protocol-mandated procedures
- Seriousness
- Action taken
- Outcome

Whenever possible, a unifying diagnosis should be reported as opposed to a listing of individual symptoms. However, symptoms should be grouped into a diagnosis only if each sign or symptom is a medically confirmed component of that diagnosis as evidenced by current standard medical textbooks. If any aspect of a sign or symptom does not fit into a classic pattern of the diagnosis, the individual symptom should be reported as a separate AE.

A preexisting medical condition is one that is present during the screening period for this study. Such conditions should be recorded as General Medical History and Baseline Conditions. A preexisting medical condition should be recorded as an AE only if the frequency, severity, or character of the condition worsens during the study.

For hospitalizations or surgical or diagnostic procedures, the illness leading to the surgical or diagnostic procedure should be recorded as the SAE, not the procedure itself. The procedure should be captured in the narrative as part of the action taken in response to the illness.

When reporting an SAE of progression of the disease under investigation, specific manifestations of the progression (e.g., acute coronary syndrome, acute pulmonary edema) should be reported, rather than the general term "disease progression."

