Any emergent laboratory abnormality (e.g., clinical chemistry or hematology) or other abnormal assessment findings (e.g., ECG or vital signs) that meets any of the following criteria should be recorded as an AE or SAE:

- Associated with clinical signs and/or symptoms
- Requires medical or surgical intervention
- May require a change in current therapy, and leads to study treatment discontinuation, delay, or interruption
- Otherwise clinically significant as determined by the Investigator

Whenever possible, the clinical diagnosis, rather than the laboratory result, should be reported by the Investigator (e.g., anemia versus low hematocrit).

Emergent and clinically significant abnormal laboratory values occurring during the study will be followed until repeat tests return to normal, stabilize, or are no longer clinically significant.

Laboratory abnormalities that are not deemed clinically significant by the Investigator should not be reported as AEs.

All deaths that occur during the protocol-specified AE reporting period, regardless of attribution, will be recorded on an eCRF and SAE report form, and expeditiously reported to the Sponsor. This includes death attributed to progression of disease.

- When recording a death on an eCRF or SAE Report Form, the event or condition that caused or contributed to the fatal outcome should be recorded as the single medical concept.
- Death is an outcome of an event. The event that resulted in death (e.g., sepsis, stroke, myocardial infarction, etc.) should be recorded in the eCRF and reported on the SAE report form.
- If the death is attributed to progression of disease, record “disease progression” as the SAE term on the SAE Report Form.
- The term “unexplained death” should be captured if the cause of death is not known. However, every effort should be made to capture the established cause of death, which may become available later on (e.g., after autopsy).

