## **VII. Safety Analyses**

All safety analyses will be performed on the Safety Evaluation Population. Analyses specific to DLAEs will use the DLAE Evaluation Population. The subjects given placebo are also included specifically to compare against JK07 such that the background disease from the treatment effects in the study population may be assessed and better discerned. All safety data will be evaluated based on Common Terminology Criteria for Analysis Events (CTCAE) Version 5.0, and listed by cohort, subject, and visit. Categorical data will be summarized in count and percentage by cohort and category.

For laboratory test results, vital signs, ECG results, weight, and body mass index (BMI), observed values and change from baseline (CFBL) will be summarized by cohort and visit using descriptive statistics.

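### The AE definition makes a judgement about heart-failure progression a condition of recording abnormal findings, so asymptomatic, untreated cardiac changes can drop out of TEAE incidence

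*Protocol*

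**What the plan says.** **Protocol 8.3.1** defines an AE as an untoward occurrence with no requirement of a causal link to treatment. Its first bullet covers abnormal laboratory, ECG, scan and vital-sign results that are "considered clinically significant in the medical and scientific judgment of the Investigator (i.e., not related to progression of underlying disease"). Its second bullet, with no exception for the disease under study, covers "Exacerbation of a chronic or intermittent pre-existing condition including either an increase in frequency and/or intensity of the condition".

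**Protocol 8.2.7** says: "Clinically significant abnormal laboratory findings are those that are not related to HFrEF or any other pre-existing condition at the time of enrollment", but adds an exception: "unless judged by the Investigator to be more severe than expected" for that subject.

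**Protocol 8.3.7** asks for an emergent abnormal finding to be recorded if it meets any one of four criteria: signs or symptoms; need for intervention; a possible therapy change that leads to study treatment being stopped, delayed or interrupted; or clinical significance otherwise, as the investigator decides. It also says that laboratory abnormalities not judged clinically significant are not to be reported as AEs. For an SAE of progression, "specific manifestations of the progression (e.g., acute coronary syndrome, acute pulmonary edema) should be reported, rather than the general term" for disease progression. For deaths it reads "If the death is attributed to progression of disease, record", and the term it then gives is that same general one.

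**Protocol 8.3.6 and Table 9** treat underlying disease as an alternative cause, weighed when relatedness of an event is assessed.

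**SAP VII** includes placebo subjects "such that the background disease from the treatment effects in the study population may be assessed and better discerned".

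**The concern.** Whether a finding is recorded and what caused it are separate questions. The gloss in 8.3.1 merges them: a finding attributed to heart-failure progression is by definition not clinically significant, and so need not be recorded as an AE. Attribution is then settled subject by subject before any comparison with placebo, although that comparison is the SAP's stated means of separating background disease from drug effect.

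This matters more here than in many first-in-human trials because the nonclinical signals were cardiac. Section 4.2 reports QTca prolongation, myocardial degeneration and raised troponin in monkeys, and links the last two: "Since the increases in cTnI could potentially be correlated with microscopic findings of myocardial degeneration", the study monitors a wide biomarker panel. Such changes can first appear without symptoms, and in a patient with HFrEF they can plausibly be read as the underlying disease. TEAE incidence and severity is the first-listed primary endpoint.

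**Working it through.** The plan states no figure on this point, so there is nothing to reproduce. The check is to follow each kind of finding through the rules.

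| Finding attributed to HF progression | Rule that applies | Recorded as an AE? |
|---|---|---|
| Symptomatic, or needing intervention | 8.3.7, first two criteria | Yes |
| Recognised exacerbation of HF | 8.3.1 second bullet; 8.3.7 on worsening pre-existing conditions | Yes |
| SAE or death from progression | 8.3.7 | Yes |
| Laboratory result more severe than expected | 8.2.7 exception | Yes |
| Other laboratory result, asymptomatic and untreated | 8.2.7 condition; 8.3.7 bars reporting if not clinically significant | No, unless read as an exacerbation |
| ECG or vital-sign change, asymptomatic and untreated | 8.3.1 gloss; 8.3.7 residual criterion | Can be left out, unless read as an exacerbation |

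In the last two rows the only open route in the 8.3.7 list is its residual criterion, clinical significance in the investigator's view. That leads back to the gloss. The exacerbation bullet points the other way, so two sites could treat the same silent change differently and both comply.

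**What else would show these findings**

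- Laboratory tests: SAP VII.C summarises values and changes and lists every result. Its shift tables use the investigator's split of abnormal results into clinically significant or not, so the 8.2.7 condition carries into that split. The result still counts as abnormal.
- Vital signs: SAP VII.D summarises values and changes and lists them by subject. The SAP's Changes from Protocol section drops the abnormal vital-sign table and listing, and relies on AE recording for clinically significant ones.
- ECG: SAP VII.G gives QT/QTcF categories and shifts, separately for the Central Reader and the investigator.
- Rhythm: SAP VII.H compares clinically significant telemetry arrhythmias with placebo and lists all subjects with a rhythm abnormality.
- Troponin and CPK-MB: exploratory endpoints, summarised and listed under SAP X. The summary visits named there omit the 4-, 8- and 12-hour samples on Day 1 and the Day 3 sample.

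**Illustration of sensitivity (assumed rates, not evidence of loss)**

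Section 4.2 gives 1 + 3 = 4 JK07 subjects in a standard cohort and 1 + 6 = 7 in an expanded one. Leaving out a single event changes 1/4 = 25% to 0/4 = 0%, or 1/7 = 14.3% to 0/7 = 0%.

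Let p be the true rate of silent findings of this kind and m the share dismissed as HF. Both are assumptions. The chance of at least one recorded event among n subjects is 1 − (1 − p(1 − m))^n. For n = 4, p = 0.20:

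- m = 0: 1 − 0.80^4 = 59.0%
- m = 0.50: 1 − 0.90^4 = 34.4%

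| n | p | m = 0 | m = 0.25 | m = 0.50 |
|---|---|---|---|---|
| 4 | 0.10 | 34.4% | 26.8% | 18.5% |
| 4 | 0.20 | 59.0% | 47.8% | 34.4% |
| 4 | 0.30 | 76.0% | 63.9% | 47.8% |
| 7 | 0.10 | 52.2% | 42.1% | 30.2% |
| 7 | 0.20 | 79.0% | 67.9% | 52.2% |
| 7 | 0.30 | 91.8% | 83.2% | 67.9% |

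**The case against.** The strongest reply is that the gloss is one phrase among several broader rules. The bullets in 8.3.1 illustrate a wide definition; 8.3.7 needs only one criterion to be met; 8.2.7 keeps results worse than expected and speaks of conditions present at enrollment; and section 8.3.12, headed as disease-related events that do not qualify as AEs, exempts none. All of this stands, and it confines the gap to asymptomatic, untreated findings.

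A reader might infer more than the documents support:

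- *That such a finding can never become a DLAE, so escalation is compromised.* Section 4.6 starts from AEs at least possibly related to IP, but also lets the DRC name an abnormality as a DLAE. The DRC reviews emerging clinical, laboratory and cardiac safety data and may act on other safety concerns. DLAE is not a listed primary endpoint. Nor would the fix alter the DLAE guidance: an event explained by clinical status fits the unlikely-related category of Table 9 and still falls outside that starting point.
- *That AE recording is the only capture of abnormal vital signs.* SAP VII.D summarises and lists them all.
- *That the comparison with placebo is lost.* Changes from baseline in ECG, laboratory tests and vital signs are separate primary endpoints, not filtered by attribution.
- *That progression deaths go missing.* They are reported whatever the attribution. The conflict is only over the term used.
- *That knowing the sentinel's treatment biases recording towards omission.* It could equally raise suspicion of the drug.

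What the objection does not remove is the direct conflict between the gloss and the rules around it.

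**Conclusion.** The wording is internally inconsistent and should be corrected. As written, it lets a judgement about disease progression decide whether an abnormal finding enters the AE record. The effect is on TEAE incidence, and on the clinically-significant split in the laboratory shift tables, for asymptomatic, untreated findings attributed to heart failure. It does not extend to all safety capture.

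The number of events lost cannot be computed. The percentages above rest on assumed values of p and m; they show that cohorts of 4 or 7 active subjects are sensitive to even one omission, not that omission occurs. The conclusion assumes that some sites will apply the gloss literally, which the text permits. The mismatch over progression deaths is a minor, separate point of terminology.

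**What to change.** 1. In Protocol 8.3.1, delete the parenthetical that equates clinical significance with being unrelated to disease progression.
2. In Protocol 8.2.7, delete the condition that a clinically significant laboratory finding be unrelated to HFrEF or another pre-existing condition.
3. State in both places that clinically significant worsening from baseline is recorded as an AE whatever the suspected cause. Relation to study drug or to underlying HF is then recorded separately using Table 9.
4. In Protocol 8.3.7, reconcile the two instructions on terms, so that the rule on specific manifestations and the rule on progression deaths agree.

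The cost is protocol wording and CRF completion guidance, plus more background heart-failure AEs in both arms. The pooled placebo group gives a reference for that background. Investigator discretion over clinical significance remains, and the DLAE guidance in 4.6 is unaffected.

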### **8.3.2 Serious Adverse Events**

An SAE is defined as an event that, at any dose, meets any of the criteria in Table 7.

**Table 7      Definitions of Serious Adverse Events**

Criteria	Description
Fatal:	The AE resulted in death
Life-threatening:	The AE placed the subject at immediate risk of death. (This classification does not apply to an AE that hypothetically might have caused death if it had been more severe)
Hospitalization/prolongation of hospitalization:	The AE resulted in hospitalization or prolongation of hospitalization
Disability/incapacity:	The AE resulted in a disability, significant incapacity, or substantial disruption of the subjects' ability to conduct normal life functions
Congenital anomaly/birth defect:	The AE was an adverse outcome in a child or fetus of a subject exposed to the study treatment regimen before conception or during pregnancy
Medically important	The AE was a medically important event that did not meet any of the above criteria, but may have jeopardized the subject and may have required medical or surgical intervention to prevent one of the outcomes listed above (examples include allergic bronchospasm that required treatment in an emergency room, seizures that do not result in hospitalization, or blood dyscrasias)

This SAE classification does not apply for the following hospitalizations:

- Admissions for social or situational reasons (e.g., no place to stay, live too far away to come for hospital visits) in the absence of any clinical AE
- Admissions at the discretion of the Investigator
- Admissions for elective or pre-planned treatment or procedure for a pre-existing condition that is unrelated to the condition under study and has not worsened since providing informed consent
- Admissions for routine treatment (e.g., platelet transfusion, IV diuresis) or monitoring of the condition under study not associated with any deterioration in condition
- Admissions for routine procedures (e.g., bone marrow aspiration, thoracentesis) associated with the disease under study
- Emergency outpatient treatment or observation that does not result in admission, unless fulfilling other seriousness criteria above

**Note:** Complications and/or prolonged admissions for routine treatment or procedure do require SAE reporting.

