Randomization u	X													

Abbreviations: 2D-TTE, 2-dimensional transthoracic echocardiography;  $\beta$ -hCG, beta-human chorionic gonadotrophin; CPK-MB, creatine kinase – muscle/brain; CPK, creatine phosphokinase; ECG, electrocardiogram; HbA1c, glycosylated hemoglobin; HDL, high density lipoprotein; hs-CRP, high-sensitivity C-reactive protein; ICD, implantable cardioverter-defibrillators; IP, investigational product; LDH, lactate dehydrogenase; LDL, low density lipoprotein; PK, pharmacokinetic.

a Subjects should be admitted in the hospital study unit by 7:00 AM, or as early as practicable, on Day 1. The subject should arrive fasted (at least 10-hour fast). All baseline clinical and laboratory assessments should be conducted prior to light breakfast/snack being provided to the subject. Subjects will be scheduled for discharge on the morning of Day 3.

b Subjects will be scheduled for hospital discharge on Day 3, after completion of all planned in-patient safety, PK, and exploratory PD/biomarker assessments. However, subjects may be asked to remain in the hospital study unit for more than 48 hours after the IP administration at the Investigator's discretion.

c A full physical examination will be performed at screening. An abbreviated physical examination will be conducted at all other visits. See [Section 8.2.1](#). During screening all subjects must verify they have no prior history of malignancy and/or have undergone cancer screening or undergo cancer screening according to American Cancer Society Guidelines ([Appendix 1 Cancer Screening Guidelines](#)).

d Women of childbearing potential only.  $\beta$ -hCG blood test at screening, urine dipstick test upon admission on Day 1 prior to IP administration to confirm absence of pregnancy, and urine specimens at all time points thereafter.

e See [Section 8.2.2](#) for assessment times and parameters.

fAll AEs, including SAEs will be collected from the time of study enrollment and until 30 days after the IP administration. Following the first 30 days, only SAEs deemed at least possibly related to the study drug or study procedures should be collected. Refer to [Table 9](#) for additional details.

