### 8.2 Safety Assessments

Planned time points for all safety assessments are provided in Table 1, and Table 2, and Appendix 3, Table 13 and Table 14.

Subjects will be observed for injection site reactions until Day 4 following IP administration, for DLAEs until Day 15 following IP administration, and for AEs and SAEs from the time of informed consent until 30 days after the IP administration. Following Day 30, only SAEs deemed at least possibly related to the study drug or study procedures will be collected until the End of Study visit (Day 180).

The safety of JK07 in patients with heart failure with reduced ejection fraction will be evaluated based on criteria described by the CTCAE Version 5.0.

The investigator will monitor the occurrence of all AEs during the first 30 days after administration of the study drug. All AEs must be recorded in the source documents and on the appropriate page(s) of the case report form. All SAEs including any deaths, which occur up to and including 30 days after administration of the study drug, must be reported to the Medical Monitor within one working day, whether or not considered causally related to the study drug. Following the first 30 days, only SAEs deemed at least possibly related to the study drug or study procedures should be collected and reported as such. All AEs and SAEs will be followed until resolution, stabilization, until the event is otherwise explained, until the end of their participation in the study, or until the subject is lost to follow-up.

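### The SAE exemption for admissions at the investigator's discretion has no limiting condition and conflicts with the hospitalization criterion in Table 7

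*Protocol*

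**What the plan says.** Protocol Section 8.3.2 calls an event serious if it meets any row of Table 7. The hospitalization row reads "The AE resulted in hospitalization or prolongation of hospitalization". Below the table, a list of six exemptions opens with "This SAE classification does not apply for the following hospitalizations". The second exemption is, in full, "Admissions at the discretion of the Investigator".

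Three other places bear on how that exemption works:

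- Table 1, footnote b, plans discharge on Day 3 but allows subjects to "remain in the hospital study unit for more than 48 hours after the IP administration at the Investigator's discretion".
- Protocol Section 8.2 sets the late collection rule: "Following the first 30 days, only SAEs deemed at least possibly related to the study drug or study procedures should be collected". Sections 4.1 and 8.3.3, Table 1 footnote f, and the SAP (Sections IV.A and VII.B) say the same in substance.
- Protocol Section 8.3.3 requires SAEs to be reported within 24 hours of the investigator becoming aware of them. SAP Section VII.B plans separate SAE tables and listings.

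**The concern.** An admission for an adverse event is commonly a physician's decision. An exemption that turns only on the investigator's discretion, without saying that no AE may be involved, can therefore absorb the criterion it is meant to refine. Two sites could classify the same admission differently, and each could point to the text.

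Seriousness decides expedited reporting and entry in the SAE tables. After Day 30 it also helps decide whether an event is collected at all. This is a first-in-human study in heart failure with safety as its primary objective, and Protocol Section 2.3 cites the potential for extended cardiovascular effects. A possibly related late admission is therefore an event the study would want on record.

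**Working it through.** The plan gives no figure to reproduce, and the sample size has no statistical basis. The check is a comparison of texts, followed by simple arithmetic on size.

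**Step 1: compare the exemptions.** The six bullets under Table 7 are limited as follows.

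- Social or situational admissions: only "in the absence of any clinical AE".
- Investigator discretion: no limit.
- Elective or pre-planned care: the condition must be unrelated to the one under study and one that "has not worsened since providing informed consent".
- Routine treatment or monitoring of the disease: no deterioration may be involved.
- Routine procedures: limited by type of admission.
- Emergency outpatient care without admission: does not apply if another seriousness criterion is met.

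Four of the other five carry an explicit condition and the fifth is limited by type. Only the discretion bullet is open.

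**Step 2: look for a limit elsewhere.** The note closing the list restores SAE reporting for complications and prolonged admissions, but only those tied to routine treatment or a routine procedure. Protocol Section 8.3.7 says which term to record when there is a hospitalization, not when an admission is serious. The SAP adds no rule. Nothing in either document narrows the bullet.

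**Step 3: trace the consequence.** Take an AE that leads to admission and meets no other row of Table 7.

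- Onset up to Day 30: all AEs are collected, so it is recorded with grade and causality. What is lost is the serious flag, the 24-hour report and the entry in the SAE tables.
- Onset after Day 30, judged unrelated: not collected, with or without the bullet.
- Onset after Day 30, judged at least possibly related: collected if serious, not collected if non-serious. This is the added loss.

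The restricted window is 180 − 30 = 150 days, and 150/180 = 83% of follow-up.

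**Step 4: size in a dose group.** Per Protocol Section 1.1, a 5-subject cohort has 1 sentinel + 3 randomized = 4 subjects on JK07, and a 9-subject cohort has 1 + 6 = 7. One subject whose only SAE is reclassified moves SAE incidence by 1/4 = 25 or 1/7 = 14.3 percentage points. If sentinels were left out because the Safety Evaluation Population is defined by randomization (SAP Section V.K), the shifts would be 1/3 = 33.3 or 1/6 = 16.7 points.

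**Step 5: extended stays.** Footnote b uses the same discretion wording, but for subjects already in hospital for dosing. Table 7 covers prolongation as well as admission, while the bullet speaks of admissions. Taken strictly, a stay extended because of an AE remains an SAE. Yet the sentence introducing the list refers to hospitalizations in general, and the shared wording invites a site to apply the exemption. The documents do not settle it.

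**The case against.** The strongest reply is that the bullet was probably meant for observation stays without an AE, and that little is lost even on a literal reading. Much of this stands.

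- An event that is fatal, life-threatening, disabling or medically important is still serious under its own row, and the last of these would catch many admissions caused by an AE. This stands on the any-criterion rule of Section 8.3.2. The words introducing the exemptions, however, do not say whether they lift the hospitalization row alone or the whole classification, and only the emergency-outpatient bullet expressly preserves the other criteria.
- A reader might infer that any AE-related admission after Day 30 goes unrecorded because of this bullet. The documents do not support that. Unrelated SAEs are outside collection then anyway, AEs that began earlier continue to be followed (Section 8.2), and concomitant treatment and scheduled examinations continue to the final visit (Section 6.5, Table 1).
- A reader might infer that dose escalation or the TEAE endpoint is undermined. The minimum escalation review runs through Day 15, when all AEs are collected. The dose-limiting guidance in Section 4.6 does not depend on the serious flag, and Section 8.3.12 has the Data Review Committee evaluate all AEs. TEAE incidence and severity up to Day 30 are unchanged.
- A reader might infer that footnote b falls squarely within the bullet. It describes remaining in hospital, not being admitted, so the most that can be said is that the classification is unclear.
- The shifts of 25 or 14 points describe any single event in a small group. The documents give no frequency for such admissions and no evidence of variation between sites.

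What the reply does not remove is the contradiction itself: intent is not stated, and the text allows the literal reading.

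**Conclusion.** The bullet conflicts with the hospitalization row of Table 7, and no other text resolves the conflict. Its effect is narrow: it reaches only AEs for which hospitalization is the sole seriousness criterion. For those, it can change SAE counts and expedited reporting up to Day 30. Over the remaining 150 or so days it can also remove new, at least possibly related events from AE and SAE collection. One affected subject shifts a JK07 group's SAE incidence by 25 or 14 percentage points, assuming sentinels are counted. How often this would happen cannot be estimated from the documents.

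This should be fixed. It does not by itself put the escalation decisions or the TEAE endpoint in doubt.

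**What to change.** Delete the bullet, or attach the condition that the first exemption already uses, "in the absence of any clinical AE". Add two sentences to Section 8.3.2: that a stay prolonged beyond the planned Day 3 discharge because of an AE meets the prolongation criterion in Table 7, and that an exempted hospitalization is still an SAE if the event meets any other row. Cross-refer to Table 1 footnote b so that the two uses of discretion are not confused, and carry the wording into the instructions for completing SAE forms.

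This changes event classification only. The cost is a short protocol edit and probably a few more SAE reports.
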